2 INTRODUCTION

It is anticipated that more than 40% of contact lens wearers would benefit from a contact lens that corrects astigmatism, but this target is not reached in most countries.¹ As new lenses come to market it is of interest to compare the performance of the new product to the performance of established products. The goal of this study is to compare the performance of Biofinity toric (Lens A), a silicone hydrogel monthly replacement lens from CooperVision Inc., which has successfully been established on the market with TOTAL30 for astigmatism (Lens B), a SiHy monthly replacement lens recently launched by Alcon Inc.

3 OBJECTIVES

To compare the clinical performance of Biofinity toric versus Total 30 for astigmatism in habitual lens wearers, when worn for 1-month each.

The primary outcome variable:

• Ease of handling for lens removal (0 - 100) reflecting a typical day in the past month, collected at the 1-month in-office visits

The secondary outcome variable:

Distance Visual Acuity (Snellen converted to logMAR) for study lenses determined at the
 1-month in-office visits

Other outcome variables:

- o Lens fit: centration, lens orientation, post blink movement at 1-month follow-up
- Subjective ratings:
 - At-home questionnaires [collected on Days 7, 14 and 27 (study CL)]
 - In-office experience ratings after lens insertion [collected at lens dispense visit (study CL)]
 - In-office experience ratings a typical day in the past week [collected at screening (habitual CL) and 1-month follow-up visits (study CL)]
 - In-office satisfaction ratings a typical day in the past week [collected at screening (habitual CL) and 1-month follow-up visits (study CL)]
 - In-office agreement ratings— a typical day in the past week [collected at screening (habitual CL) and 1-month follow-up visits (study CL)]
 - In-office preference ratings collected at exit visit (study CL)

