5.5 SCHEDULED AND UNSCHEDULED VISITS

This study has a minimum of 4 scheduled study visits, including the screening visit. There is an option for repeated screening visit if needed.

A scheduled 1-month follow-up visit may only take place when the participant attends wearing the study lenses for at least two hours that day. If this is not the case and the participant is not experiencing any problems with the lenses, the appointment will be rescheduled, ideally within the visit window.

Visits that fall outside of the specified visit windows will be designated as protocol deviations and at the end of the study, the data collected during protocol deviations will be assessed for their suitability to be included in the analysis population.

Table 3 summarizes the scheduled study visits and study codes.

Table 2: Summary of visits

Visit code	Approximate Duration	Visit Description
0	2 hrs	Screening, Habitual baseline (collect in-office ratings for subjective experience, satisfaction and agreement questions) & Fitting of study lenses
0/R1, 0/R2	As needed	Repeat Visit 0 if needed
1-0	0.75 hr	Dispense Lens type #1 (0-28 days after Visit 0); collect in-office subjective ratings after 10 mins of lens insertion; provide at-home diaries
2-0	1.5 hr	1-month follow-up Lens type #1 (28-32 days after 1-0); review at-home diaries; collect in-office ratings for subjective experience, satisfaction and agreement questions for Lens type#1
		Dispense Lens type #2; collect in-office subjective ratings after 10 mins of lens insertion; & Provide at-home diaries
3-0 and exit	1.5 hr	1-month follow-up Lens type #2 (28-32 days after 2-0); review at-home diaries; collect in-office ratings for subjective experience, satisfaction and agreement questions for Lens type#2; collect preference ratings between Lens type#1 and Lens Type#2
		Exit forms & remuneration

Visits 1-0 (Dispense Lens type #1) and 2-0 (Dispense Lens type #2) will count as day 0 Lens type #1 and #2 will be either Lens A or B, as determined by the randomization table.

[figure not shown]

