5.5.6 STUDY EXIT

The study exit form will be completed when a participant exits the study. This form will be completed either after the last study visit, or if the participant is discontinued from the study at another time, complete also an unscheduled visit form. A study exit form must be completed for all participants who have taken a study ID number. If in the opinion of the investigator post-study follow-up visits are required, the exit form will be completed after the last follow-up visit.

Exit visual acuity will be recorded with either the participant's spectacles, refraction or habitual contact lenses. An exit biomicroscopy assessment will be conducted if not already completed on the same day for a concurrent study visit.

After the exit assessments have been completed, the participant and investigator will complete the study completion and remuneration forms. At this time the participant will be considered as having exited the study.

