5.5.7 UNSCHEDULED VISITS

An unscheduled visit is defined as an interim visit requested by the participant or investigator due to an unanticipated problem. Data recorded at these visits will be entered into the database. Only relevant and applicable unscheduled visit information will be included in the final report as deemed necessary.

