5.6 STUDY PROCEDURES

Table 4 summarizes the procedures conducted at each visit.

Table 3: Summary of procedures to be conducted at scheduled visits

	0 Screen Fit & order study CL	1-0 Dispense first study lens	2-0 1-month follow- up first study lens, dispense second study lens	3-0 1-month follow- up second study lens	Exit
Consent process	x				
Subject age & sex	x				
CL history and/or lens wear schedule	х		х	х	
Health & medication	x	Х	Х	Х	

	0 Screen Fit & order study CL	1-0 Dispense first study lens	2-0 1-month follow- up first study lens, dispense second study	3-0 1-month follow- up second study lens	Exit
Review any problems with eyes/study lenses	Study OL	х	lens X	х	
	х				X (or V1 subj. refraction result)
	Х				
	х				
Study lens fitting	Х				
Dispense study CLs		Х	Х		
	Х	Х	Х	Х	
	Х	Х	Х	Х	
	Х		Х	Х	
	Х		Х	Х	
				Х	
	Х		Х	Х	
		Х	Х		
			х	х	
	х	х	х	х	X (unless completed at concurrent visit)
Study completion and Exit					Х

¹ High Contrast High Illumination

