12 STATISTICAL ANALYSIS AND DATA MANAGEMENT

12.1 STATISTICAL ANALYSIS

All data will be analyzed by CORE at the University of Waterloo. Unmasked data analysis will be conducted using Statistica 14.0, Statsoft or other suitable software. Descriptive statistics will be provided on demographic data (age, gender, refractive error distribution, etc.). Table 7 lists the primary and other outcome variables and anticipated statistical procedures.

Visual acuity results will be converted to LogMAR for analysis purposes.

Comparisons will be made between the study lenses for the variables measured at the 1-month visits. Additionally, the subjective ratings completed on days 7, 14 and 27 with each study lens will be compared. A binomial test will be used to analyze the results for the count data of subjective preferences and experience responses. Where relevant, the number of "no preference" responses will be evenly distributed to the two options on the basis they would be equally likely to choose either.

For assessments conducted for each eye separately, the right eye will be used for analysis. If a general difference is found (paired t-test / Wilcoxon matched pairs) between OD and OS, a comment will be provided.

Where appropriate, data may be presented as both mean or median and as counts by 'bucket' groups.

Additional analysis may be conducted.

Table 6: Statistical procedures

Variable	Analysis	Statistical test
	Comparison between study lenses	Freidman ANOVA
	and time points	Wilcoxon matched pairs test
	Comparison between study days	Freidman ANOVA
	and/or between contact lenses per	Wilcoxon matched pairs test
	time point.	RMANOVA
Demographics,	Descriptive stats	One or more: mean,
lens fit variables		median*, mode, standard
		deviation, minimum,
		maximum, frequency count

^{*} For non-parametric data only

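### Does the plan lose the primary ease-of-removal rating for participants who stop a lens early?

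*Combined protocol and SAP*

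**What the plan says.** Section 3 defines the primary outcome as "Ease of handling for lens removal (0 - 100) reflecting a typical day in the past month, collected at the 1-month in-office visits" and states the objective as a comparison of the two lenses "when worn for 1-month each". Section 12.1 adds: "Comparisons will be made between the study lenses for the variables measured at the 1-month visits". The tests listed there are within-participant (Friedman, Wilcoxon matched pairs, repeated-measures ANOVA), although the variable names in those rows cannot be read.

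Under section 5.5 a scheduled 1-month visit "may only take place when the participant attends wearing the study lenses for at least two hours that day". A participant who falls short of that but has no lens problem is rescheduled. Data from visits outside the window are assessed at the end of the study for inclusion in the analysis population.

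For early exit, section 5.5.6 requires the exit form and says that "if the participant is discontinued from the study at another time, complete also an unscheduled visit form". It also names visual acuity and biomicroscopy. Section 5.5.7 states: "An unscheduled visit is defined as an interim visit requested by the participant or investigator due to an unanticipated problem". It continues: "Data recorded at these visits will be entered into the database". Section 9 lists reasons for discontinuation, lets participants who stop withdraw their data, and has all discontinuations reported with reasons.

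The sample size in section 5.3.1 is 44 completers from up to 48 dispensed, with an SD of 20 on the 0-100 scale.

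**The concern.** Read in sequence, these sections seem to leave a hole. The primary rating is tied to the 1-month visits. Those visits require the lens to have been worn that day, and a person who has given up a lens cannot meet that condition. Yet recalling how easy a lens was to remove needs no lens on the eye. Section 5.5.6 mentions no rating at exit, and the readable part of section 12.1 gives no rule for a participant with only one lens rated.

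What is at stake is bias more than power. If people leave because they do badly with one lens, the pairs that remain are those who tolerated both, and the lens that drove people out looks better than it should. A rating not requested at exit is hard to obtain afterwards, and a list of reasons for stopping supplies no score. The sponsor's own lens is being compared with a competitor's, so a reader would want to know whether losses favoured one side.

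**Working it through.** **1. The plan's own figure.** Section 5.3.1 gives 90% power, SD 20 and n = 44, but no readable effect size, alpha or sidedness, so 44 can only be back-solved. Assume a paired comparison, two-sided alpha 0.05, SD of differences 20 and a difference of 10:

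- Normal approximation: (20 × (1.960 + 1.282) / 10)² = 42.0, so 43.
- Noncentral t: 44, with power 90.0%.

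A one-sided test with a difference of 9 also gives 44, so the inputs are not unique. The loss allowance is 4/48 = 8.3%, and 44 / (1 − 4/48) = 48. Power for the planned loss is therefore covered.

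**2. Possible shift from early stoppers.** Let *a* participants stop one lens and *b* the other, with *a* + *b* = 4. Each would have rated the stopped lens *g* points worse, and the 44 completers show no difference. The mean over all 48 then differs from the completers' mean by

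shift = (*a* − *b*) × *g* / 48.

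| Split | g = 20 | g = 30 | g = 40 |
|---|---|---|---|
| 4-0 | 1.67 | 2.50 | 3.33 |
| 3-1 | 0.83 | 1.25 | 1.67 |
| 2-2 | 0 | 0 | 0 |

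If completers instead favour the stopped lens by 10 points, a 4-0 split with *g* = 30 gives (44 × 10 − 4 × 30) / 48 = 6.67, a shift of 3.33. What matters at 4-0 is the distance between stoppers and completers, here 40 points.

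**3. Against the standard error.** With 20 as the SD of paired differences, SE = 20 / √44 = 3.02. The 4-0 shifts are 0.55, 0.83 and 1.11 SE. A shift of one SE needs

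- 4-0: *g* = 3.02 × 48 / 4 = 36.2 points;
- 3-1: *g* = 3.02 × 48 / 2 = 72.4 points.

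The document does not say whether 20 is the SD of differences or of one lens's ratings. If it is per lens, the SD of differences is 20 × √(2(1 − ρ)). That is 28.3 at ρ = 0 and 14.1 at ρ = 0.75, so the SE is 4.26 or 2.13 and the 4-0 threshold is 51.2 or 25.6 points. At ρ = 0.5 it is unchanged.

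**4. How likely are the splits?** If each of four losses is equally likely to fall on either lens, the chances are 2/16 = 12.5% for 4-0 either way, 8/16 = 50% for 3-1 and 6/16 = 37.5% for 2-2. In 87.5% of cases the shift is therefore at most 1.67 points (0.55 SE), even with *g* = 40.

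**5. Can the text show that the rating is missing?** The caption in section 5.6 reads "Table 3: Summary of procedures to be conducted at scheduled visits", so that table does not govern unscheduled visits, and most of its row labels are blank. Most numbered steps for Visits 2-0 and 3-0 are also blank. The exit and unscheduled visit forms are not reproduced, and the items on the day 7, 14 and 27 home questionnaires cannot be seen. Nor is section 5.5.6 a full list of exit data: section 3 places preference ratings at the exit visit, and section 5.5.6 does not mention them. The section 5.5 visit table attaches that item to the final scheduled visit, so it does not prove that ratings are taken at early exit. It does show that silence in section 5.5.6 is weak evidence.

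**6. Does the two-hour rule block an early rating?** It applies to a scheduled 1-month visit. An early rating would be taken at an exit or unscheduled visit, which the rule does not govern. For a wearer without problems it delays the rating but does not lose it.

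**The case for a change.** The best case for acting is that the cost is low: one form item if it is absent, one sentence, and one sensitivity analysis, with the primary analysis and sample size untouched. Section 9 foresees stopping for poor comfort or vision, symptoms and adverse events, so lens-related loss is not fanciful. In a 4-0 illustration with no difference among completers, a mixed model fitted without early ratings recovers none of the shift, so later modelling cannot replace collecting the rating. Section 12.1 also describes an unmasked analysis, which makes handling rules fixed in advance more attractive.

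Part of this stands. The readable text does not say what happens to the rating at early stopping, and asking the sponsor is reasonable. It does not carry the case for a change. Early ratings reflect less than a month of wear and so answer a somewhat different question. First-month stoppers still have no pair, and those lost to follow-up or withdrawing their data stay missing. The analysis would gain about four people at most. The performance reasons that section 9 names are comfort and vision, not removal; other listed reasons, such as relocation, have nothing to do with the lens. Testing the final prescription on eye (section 5.4) should limit early fit and vision failures. Discontinuations are already reported with reasons, and section 12.1 leaves room for additional analyses.

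**Conclusion.** No change to the plan is called for. Whether the rating is taken at early stopping lies in material absent from the public text, so an omission cannot be inferred; the sponsor could settle it by checking the exit and unscheduled visit forms. A paired comparison of those who wore each lens for a month matches the objective and is a defensible primary analysis.

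Bias is possible but not demonstrated. With the planned four losses it exceeds one standard error only if all four fall on one lens and their gap is above about 36 points (26 to 51 if 20 is a per-lens SD with correlation 0.75 to 0), or at 3-1 if the gap is above about 72. Nothing in the documents supports gaps of that size. The conclusion assumes losses near the planned 8.3%; heavier loss concentrated on one lens would matter more. The mean shift is only a guide to scale, since the listed tests include rank methods. That the primary test is paired is itself inferred from the cross-over design and the tests listed.

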4 HYPOTHESIS

The null hypothesis is that there will be no difference for the primary outcome variable between Lens A compared to Lens B.

5 MATERIALS AND METHODS

5.1 STUDY DESIGN

5.1.1 OVERALL DESIGN

This study will be conducted at several optometry practices in the US and Canada. This study is a prospective, bilateral eye, subjected-masked, randomized, 1-month cross-over, daily-wear design involving two different silicone hydrogel toric lens types. Each lens type will be worn bilaterally for approximately one month, during which participants record their subjective lens-wear experience on three different days. Additional measures will be collected during in-office study visits.

5.1.2 RANDOMIZATION

A randomization schedule will determine the order of Lens A and Lens B wear for the first/second month for each participant. Participants will be randomized immediately prior to their first lens dispense.

This randomization schedule will be generated for each site using a web-based program: (www.randomization.com). The lens type that will be worn during the first month is called "Lens type #1", the lens type dispended for the second month is called "Lens type #2". The final study randomization schedule will be generated by CORE's Database Administrator and provided to the research assistants at each site.

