5.1.3 MASKING

At the fitting visit, only the participant will be masked of the lens type, the investigator will know which type is fit to make changes to the lens at this visit if needed. Strongly adhesive stickers will be placed on the packages/foils to mask the participant to the lens brand. At both dispense visits, participants will be masked to the lens type dispensed. The study personnel will determine the lens order according to the randomization schedule and will over-labeled the lens packages/foils prior to dispense.

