5.3.3 INCLUSION AND EXCLUSION CRITERIA

A person is eligible for inclusion in the study if he/she:

- 1. Is between 18 and 39 years of age (inclusive) and has full legal capacity to volunteer;
- 2. Has read and signed an information consent letter;
- 3. Self-reports having a full eye examination in the previous two years;

- 4. Anticipates being able to wear the study lenses for at least 8 hours a day, 6 days a week;
- 5. Is willing and able to follow instructions and maintain the appointment schedule;
- 6. Habitually wears of toric soft contact lenses binocularly.
 - a. No more than 1/3 of the participants should be wearing daily disposable soft toric lenses:
 - b. the remaining 2/3+ of the participants must be planned frequent replacement soft toric lens wearers as follows^:
 - i. TOTAL30 for Astigmatism: maximum of 3 (~10%) (no target percentage)
 - ii. Biofinity toric: maximum of 13 (~40%) (PLUS a target of minimum 10 (~30%))
 - iii. Air Optix for Astigmatism (inclusive of +Hydraglyde): maximum of 10 (~30%) (PLUS a target of minimum 7 (~20%))
 - iv. ULTRA for Astigmatism: maximum of 5 (~15%) (no target percentage)
 - v. Acuvue Vita for Astigmatism: maximum of 3 (~10%) (no target percentage)
 - vi. Acuvue Oasys for Astigmatism: maximum of 10 (~30%) (no target percentage)
 - vii. Other brands of frequent replacement: maximum of 7 (~20%) (no target percentage)
- 7. Has refractive astigmatism of at least -0.75DC but no more than -2.75DC in each eye that is correctable with a soft toric lens with a cylinder power of no greater than -2.25DC;
- 8. Is ammetropic and requires a spectacle spherical component of +8.00 to -10.00D inclusively;
- 9. Can be fit and achieve binocular distance vision of at least 20/32 Snellen with the available lens parameters (see Table 1).

A person will be excluded from the study if he/she:

- 1. Is participating in any concurrent clinical or research study;
- 2. Has any known active* ocular disease and/or infection that contraindicates contact lens wear;
- 3. Has a systemic condition that in the opinion of the investigator may affect a study outcome variable;
- 4. Is using any systemic or topical medications that in the opinion of the investigator may affect contact lens wear or a study outcome variable;
- 5. Has known sensitivity to the diagnostic sodium fluorescein used in the study;
- 6. Self-reports as pregnant, lactating or planning a pregnancy at the time of enrolment#;

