5.5.1 VISIT 0 SCREENING & FITTING VISIT

Informed consent shall be obtained in writing from the participant and the process shall be documented before any procedure specific to the clinical investigation is carried out.

Participants will be assigned a unique alpha-numeric study ID after they sign the consent documentation i.e. before their eligibility for the study has been confirmed. Each site will use a different letter preceding the participant ID number. For example, participant 01 at site P will be P01, and participant 01 at site L will be L01. Ineligible participants will be discontinued from the study.

The investigator will determine participant eligibility using the inclusion and exclusion criteria. The study procedures are outlined below:

[figure not shown]
- 1. The participant is expected to insert their habitual contact lenses at least 2 hours before attending the visit.
- 2. The participant will be required to read and sign an Informed Consent Form (Appendix 1) prior to enrollment. When the participant has signed the consent form, the participant will be considered enrolled in the study and will be assigned a study ID.
- 3. Participant demographics and medical history (age, sex, medical conditions, medications, allergies).
- 4. Contact lens history (habitual lens information and wearing habits).

10. The participant removes their habitual contact lenses.

15. The investigator will fit both study lenses (Lens A and Lens B) using trial lenses following to the manufacturers fitting guidelines.

16.

- 17. The investigator will confirm that the participant meets the eligibility specifications set out in the inclusion criteria and exclusion criteria and is eligible to continue in the study.
- 18. Schedule dispense visit (0-28 days after Visit 0) and order both study lens types in the final prescriptions (only lenses from commercial 6-pack boxes are used for dispensing) see section 5.4 for details.

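### Each site's lens-order schedule goes to site staff and no concealment is described, so whoever holds it could know the next order before a participant is dispensed

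*Combined protocol and SAP*

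**What the plan says.** Section 5.1.2 (Randomization) makes the schedule site-specific: "This randomization schedule will be generated for each site using a web-based program". It then states who receives it: "The final study randomization schedule will be generated by CORE's Database Administrator and provided to the research assistants at each site". On timing it says: "Participants will be randomized immediately prior to their first lens dispense".

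Section 5.1.3 (Masking) says who uses the schedule: "The study personnel will determine the lens order according to the randomization schedule and will over-labeled the lens packages/foils prior to dispense". The same section, on the fitting visit, states: "At the fitting visit, only the participant will be masked of the lens type".

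Section 5.5.1 (Visit 0) collects contact lens history, has the investigator fit both study lenses and confirm eligibility, and ends with: "Schedule dispense visit (0-28 days after Visit 0) and order both study lens types in the final prescriptions". The role that books the visit is not named.

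Section 5.3.2 expects about 10 dispensed participants per site. Section 5.3.3, criterion 6b, caps habitual Biofinity toric (Lens A) wearers at 13 with a target of at least 10; exceptions may be agreed with the study monitor or sponsor.

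Section 13 requires training on randomization and participant masking but does not give its content. In the public copy of section 5.5.3 (Visit 1-0), only steps 1 and 11 can be read.

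**The concern.** A randomised order protects the comparison only if those who can influence who takes the next line cannot see it. Here a site-level list of about 10 lines is in the hands of site staff, and assignment takes place at a visit that can fall anywhere in a four-week window after screening. If lines are used in list sequence, the sequence of dispense visits decides who gets which order. By then the site knows the habitual brand and how both lenses fitted.

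A crossover removes much of the usual harm, because a participant's general tendency to rate high or low cancels within that participant. It does not remove a change between months that differs by kind of participant when kind is linked to order. This could happen with the primary outcome, ease of removal: wearers new to both lenses may improve with practice, while habitual Lens A wearers may not. The issue is knowledge of the order before assignment. It is separate from whether an examiner knows the lens afterwards.

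**Working it through.** **1. What the text establishes**

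| Question | Readable text |
|---|---|
| Who generates the list? | CORE's Database Administrator (5.1.2) |
| Who receives it? | Research assistants at each site (5.1.2) |
| Who reads the order from it? | Study personnel, not further specified (5.1.3) |
| Who decides eligibility? | The investigator, at Visit 0 (5.5.1) |
| Who books the dispense visit? | Not stated (5.5.1) |
| When and in what form does the list arrive? | Not stated |
| Is concealment described? | No |

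**2. The plan's own figure**

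Section 5.3.1 gives SD 20, 90% power and 44 completers. It gives no target difference, significance level or sidedness, and does not say whether 20 is the SD of the paired difference. Assuming a 10-point difference, a paired-difference SD of 20 and a two-sided 5% test, a paired t-test needs n = 44 (power 0.900). These assumptions are consistent with the plan and are used below. SE = 20/√44 = 3.015.

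**3. A period change common to everyone**

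If everyone changes by π points between months, the crude paired lens difference is biased by π × (n_AB − n_BA)/N. With π = 5 and a 26/18 split of 44, this is 5 × 8/44 = 0.9 points. With 22/22 it is zero. Steering by participant type does no harm here if the orders are balanced.

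**4. A period change that differs by type**

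Assume 48 dispensed, 24 per order. Habitual Lens A wearers do not change between months; all others improve by d points in month 2. All k habitual Lens A wearers are in order A-B.

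- Others in B-A: 24, each contributing +d to A minus B.
- Others in A-B: 24 − k, each contributing −d.
- Bias = [24d − (24 − k)d]/48 = k × d/48, in favour of Lens A.

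Averaging the two order means, which removes a common period effect, gives the same value: [d − d(24 − k)/24]/2 = k × d/48. A simple period term therefore does not remove this bias.

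For a 75/25 split of the 13, 9.75 are in A-B and 3.25 in B-A. The net number is 6.5 and the bias is 6.5 × d/48.

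Error rates are from the noncentral t with 43 degrees of freedom and noncentrality bias/3.015, two-sided 5%.

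| Scenario | d = 3 | d = 5 | d = 10 |
|---|---|---|---|
| All 13 in A-B | 0.8 points (5.8%) | 1.4 (7.2%) | 2.7 (14.2%) |
| All of 10 in A-B | 0.6 (5.5%) | 1.0 (6.3%) | 2.1 (10.4%) |
| 75/25 split of 13 | 0.4 (5.2%) | 0.7 (5.6%) | 1.4 (7.2%) |
| No steering | 0 (5.0%) | 0 (5.0%) | 0 (5.0%) |

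The values of d and the degree of steering are assumptions; the documents give neither. The bias uses the 48 dispensed and the SE uses the 44 completers.

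**The case against.** A reader might infer that the complete list reaches, in advance, the same people who book and dispense, and hence that allocation is definitely unconcealed. The documents do not support that. They name research assistants as recipients and unspecified study personnel as users, give eligibility to the investigator, and name no scheduler. They do not say when or in what form the list arrives. If the research assistants keep it from those who book visits, the risk shrinks. The steps of Visit 1-0 at which an order would be drawn cannot be read in the public copy, so silence there proves nothing. This part of the objection stands, and limits the point to saying that no concealment is described.

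The design also limits the damage. Eligibility is confirmed and both lenses are fitted and ordered before randomisation, so foreknowledge can affect only order. Dispense dates depend partly on when the ordered lenses arrive. Masked participants rate the primary outcome. The worst case needs steering by habitual brand, in one direction, across about five sites, plus a differing period change; the documents show neither. The 14.2% figure needs a change of 10 points, as large as the lens difference assumed in reproducing the power. All of this stands, and it keeps the likely effect small.

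Concealment is not the only remedy for the modelled example: stratifying by habitual lens or fitting a habitual-lens-by-period term would deal with it. Neither appears in the readable plan, and both address only a characteristic chosen beforehand.

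Pre-randomisation confirmation of eligibility does not close the route, because the route runs through the sequence of dispense visits.

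**Conclusion.** The point holds in limited form. The stated procedure puts the order list in site hands with no described safeguard, and a better method costs little. The possible bias is conditional and mostly small: zero without steering, 0.4 to 1.4 points with a 75/25 split of 13 habitual Lens A wearers, and 0.8 to 2.7 points in the near-maximum case, for differential changes of 3 to 10 points. These figures rest on equal order sizes, a paired-difference SD of 20, and no month-to-month change in habitual Lens A wearers.

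A reader might go further and conclude that sites will steer, or that the lens comparison is biased as planned. Nothing in the documents supports either. This is a recommended, inexpensive improvement; the sample size is unaffected.

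**What to change.** Replace the last sentence of section 5.1.2 with:

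> *The schedule is held by CORE's Database Administrator and is not provided to the sites as a list. Each site receives sequentially numbered, sealed, opaque envelopes. The next envelope is opened and dated at Visit 1-0 only after eligibility is confirmed and the participant has attended. An opened order is not reassigned.*

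Section 5.1.3 should then refer to the opened envelope as the source of the lens order.

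Release of each order by CORE on request is an acceptable alternative if practical. It would need someone available during a visit planned at 0.75 hours. It should not be assumed that REDCap can do this without further set-up: section 12.2 describes it as used within CORE by authorised users, while sites work on paper and upload scans.

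The cost is one protocol paragraph and about 10 envelopes per site. No extra participants or measurements are needed.
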